8.2.1. Progressive Disease Visit

Progressive Disease visit should be performed at any time during the study, if based on clinical and/or laboratory evaluation, the Investigator suspects progressive disease, or if the subject discontinues treatment for any other reason. If possible, the visit should be performed within 24 hours after the subject's previous dose.

- Complete physical examination
- Vital signs and performance status (KPS)
- Hematology
- Serum chemistry
- Donor/host chimerism testing
- Immunosuppressant level – if applicable
- cGVHD NIH Form assessment ([Appendix F](#) and [Appendix G](#))
- Lee cGVHD Symptom Scale ([Appendix E](#))
- Photographic imaging of cGVHD
- Quantitative serum immunoglobulins (IgA, IgG, and IgM)
- Review adverse events and concomitant medications (including corticosteroid requirements)
- Review returned subject dosing diary
- Final drug accountability

8.2.2. End-of-Treatment Visit

An End-of-Treatment visit should occur 30 days (\pm 7 days) from the last dose of study drug or prior to the start of a new cGVHD treatment. If the subject starts a new cGVHD treatment less than 7 days after the Progressive Disease visit, only those procedures not conducted at the Progressive Disease visit should be performed at the End-of-Treatment visit.

The following procedures will be performed at the End-of-Treatment visit:

- Complete physical examination
- Vital signs and performance status (KPS)
- Hematology

- Serum chemistry
- Donor/host chimerism testing Lee cGVHD Symptom Scale ([Appendix E](#))
- cGVHD NIH Form assessment ([Appendix F](#) and [Appendix G](#))
- Photographic imaging of cGVHD
- Immunosuppressant level – if applicable
- Quantitative serum immunoglobulins (IgA, IgG, and IgM)
- Review returned subject dosing diary
- Review adverse events and concomitant medications (including corticosteroid requirements and any new cGVHD treatment if applicable)
- Final drug accountability
- Biomarker sampling

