7.1.6. Adverse Events

The accepted regulatory definition for an adverse event is provided in [Section 11.1](#). The occurrence of AE at the time the ICF is signed until first dose should be recorded under medical history in the eCRF form. All medical occurrences after the first dose with study drug until 30 days after the last dose of study drug that meet the adverse event definition must be recorded as AEs in the eCRF. Laboratory abnormalities designated clinically significant by the Investigator will also be documented as adverse events. Additional important requirements for adverse event and serious adverse event reporting are explained in [Section 11.4](#).

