10.5. Safety Analysis

The safety variables to be analyzed include adverse events, clinical laboratory test results (hematology and chemistry), and other safety measurements. They will be summarized by descriptive statistics. No formal statistical testing is planned.

Exposure to ibrutinib first dose and reasons for discontinuation from study treatment will be tabulated.

Adverse Events

Adverse event parameters to be evaluated are the type, incidence, and intensity of adverse events; the relationship of adverse events to ibrutinib; and the action taken with respect to ibrutinib treatment due to adverse events.

The verbatim terms used in the eCRF will be coded using the Medical Dictionary for Regulatory Activities (MedDRA).

Treatment-emergent adverse events are those adverse events occurring after the first dose of study drugs and within 30 days following the last dose of study drug; any adverse event that is considered study drug-related regardless of the start date of the event; or any adverse event that is present at baseline but worsens after the first administration of study drug in severity or is subsequently considered drug-related by the Investigator. All treatment-emergent adverse events will be included in the analysis.

For each adverse event, the percentage of subjects who experience at least 1 occurrence of the given event will be summarized. The number and percent of subjects with treatment-emergent adverse events will be summarized according to intensity (NCI CTCAE v. 4.03) and drug relationship as well as categorized by system organ class and preferred term. Summaries, listings, datasets, or subject narratives may be provided, as appropriate, for those subjects who die, who discontinue treatment due to an adverse event, or who experience a severe or a serious adverse event.

Clinical Laboratory Tests

All laboratory values will be converted to standard international units and will be graded using the [NCI CTCAE v. 4.03](#).

A summary of the shifts in selected laboratory hematology and serum chemistry parameters from baseline to the worst toxicity grade during the study will be tabulated.

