11.4.2. Adverse Event Reporting Period

All AEs whether serious or non-serious, will be documented in the source documents from the time signed and dated ICF is obtained until 30 days following the last dose of study drug. SAEs will be reported to the Sponsor from the time of ICF signing. Both serious and non-serious AEs will be recorded in the eCRF from the first dose of study drug until 30 days after the last dose of study drug.

Serious adverse events reported after 30 days following the last dose of study drug should also be reported if considered related to study drug. Resolution information after 30 days should be provided.

Progressive disease should NOT be reported as an event term, but instead symptoms/clinical signs of disease progression may be reported.

All adverse events, regardless of seriousness, severity, or presumed relationship to study drug, must be recorded using medical terminology in the source document. All records will need to capture the details of the duration and the severity of each episode, the action taken with respect to the study drug, investigator's evaluation of its relationship to the study drug, and the event outcome. Whenever possible, diagnoses should be given when signs and symptoms are due to a common etiology (eg, cough, runny nose, sneezing, sore throat, and head congestion should be reported as "upper respiratory infection"). Investigators must record in the CRF their opinion concerning the relationship of the adverse event to study therapy. All measures required for adverse event management must be recorded in the source document and reported according to Sponsor instructions.

All deaths should be reported with the primary cause of death as the AE term, as death is typically the outcome of the event, not the event itself. The primary cause of death on the autopsy report should be the term reported. Autopsy and postmortem reports must be forwarded to the Sponsor, or designee, as outlined above.

If a death occurs within 30 days after the last dose of study drug, the death must be reported to the Sponsor as a serious adverse event.

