Concomitant medications	x	Continuous from Informed Consent to 30 days after last dose of study drug									
Adverse events	x	Continuous from Informed Consent to 30 days after last dose of study drug									
Biomarkers											
T/B/NK cell counts	x ⁱ	x ⁱ	x ⁱ	x ⁱ		Week 9, 13					
Biomarkers		x			x	Weeks 13, 25	Weeks 37, 49		x		

Abbreviations: AEs=adverse events; aPTT=activated partial thromboplastin time; ECG=electrocardiogram; KPS=Karnofsky Performance Status; EOT=end-of-treatment; INR=international normalized ration; PD=pharmacodynamic; PK=pharmacokinetics; PO=orally; PT=prothrombin time; q4 weeks=every 4 weeks; q12 weeks=every 12 weeks

Footnote:

- a. Physical Examination includes: general appearance of subject, examination of skin, eyes and fundi, ears, nose, throat, lungs, heart, abdomen, extremities, musculoskeletal system, lymphatic system, and nervous system.
- b. Only a limited symptom-directed physical examination is required. Review of symptoms should include inquiry of ocular symptoms; subjects should be referred to an ophthalmologist for a formal examination if any Grade ≥ 2 symptoms are reported.
- c. Oxygen saturation by pulse oximeter is permitted. If not done, then PFT with FEV1 required within 6 months of Screening.
- d. ECG's may be performed at the Investigator's discretion, particularly in subjects with arrhythmic symptoms (eg, palpitations, lightheadedness) or new onset of dyspnea.
- e. Women of childbearing potential only. Serum pregnancy test required at Screening and urine pregnancy test required at Day 1 prior to first dose. If the test result is positive, the pregnancy must be ruled out by ultrasound to be eligible.
- f. Lee cGVHD Symptom Scale should be completed prior to any assessments, and before being clinically evaluated by the study nurse or physician.
- g. Pharmacokinetic (PK) samples will be drawn for all subjects according to the schedule in [Section 7.1.13.1](#). Additional PK samples will be collected for subjects treated with concomitant a moderate or strong CYP3A inhibitors while on ibrutinib treatment according to the schedule in [Section 7.1.13.1](#).
- h. Pharmacodynamic (PD) sampling for PCYC will be performed on selected days at predose and post-dose. Refer to [Table 3](#) for more details.
- i. T/B/NK sampling for PCYC will be performed on selected days at predose and post-dose. Refer to [Table 4](#) for more details.

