6.1 Adverse Events

The verbatim terms used in the CRF by investigators to identify adverse events (AEs) will be coded using the Medical Dictionary for Regulatory Activities (MedDRA). Adverse events will be graded by the investigator according the National Cancer Institute common terminology criteria for adverse events (CTCAE) Version 4.03.

Drug-related adverse events are those assessed by investigator as being possibly related or related to study drug.

Treatment-emergent AEs are defined as those events that 1) occur on or after the first day of study drug, and within 30 days following the last dose of study drug or initiation of subsequent cGVHD therapy; 2) any event with missing onset date and its resolution date is during the treatment phase unless the event was indicated in the CRF that was present

before the first day of study drug; 3) any event that is considered study drug-related regardless of the start date of the event; or 4) any event that is present at baseline but worsens in severity or is subsequently considered drug-related by the investigator.

For each adverse event, the percentage of subjects who experience at least 1 occurrence of the given event will be summarized. In the event a patient experiences repeat episodes of the same AE, then the event with the highest severity grade will be used for purposes of incidence tabulations.

Summaries of AEs include:

- Incidence of AEs and serious adverse events (SAEs) by System Organ Class (SOC) and preferred term
- Incidence of AEs and SAEs by preferred term
- Incidence of drug-related AEs and SAEs

AE leading to study treatment discontinuation for the subjects who discontinued study drug due to AE, AE leading to dose reduction, and AEs leading to death will be summarized.

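### After progression and an early switch to new cGVHD therapy, no scheduled contact lists an AE question for the rest of the 30-day window, and SAP 6.1 may drop events that protocol 10.5 counts (minor)

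*Protocol*

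**What the plan says.** Days are counted from the last dose of ibrutinib (Day 0).

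**Recording.** Protocol 7.1.6 covers "All medical occurrences after the first dose with study drug until 30 days after the last dose of study drug". Section 11.4.2 requires eCRF recording "until 30 days after the last dose of study drug", and the AE row of Appendix A reads "Continuous from Informed Consent to 30 days after last dose of study drug". None of these stops at new cGVHD therapy.

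**Visits.** Protocol 8.2.2 sets the End-of-Treatment visit at 30 days (±7) "from the last dose of study drug or prior to the start of a new cGVHD treatment", with no minimum interval for the early option. When new therapy follows within a week of a visit for progression, the second visit is shortened: "only those procedures not conducted at the Progressive Disease visit should be performed at the End-of-Treatment visit". AE review is on both visit lists, so it need not be repeated. Section 8.2.1 asks for the Progressive Disease visit, if possible, within 24 hours of the previous dose.

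**Follow-up after progression.** Sections 3.1 and 8.3.2 give these subjects survival follow-up, about every 3 months (±14 days), in clinic or by telephone. Appendix A has it every 12 weeks (±7 days), and that column marks survival alone.

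**Analysis.** Protocol 10.5 counts events "occurring after the first dose of study drugs and within 30 days following the last dose of study drug". SAP 6.1 counts events "within 30 days following the last dose of study drug or initiation of subsequent cGVHD therapy" and does not say which date governs. The SAP also counts "any event that is considered study drug-related regardless of the start date of the event", and protocol 10.5 has the same exemption. Both documents also count baseline conditions that worsen.

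**The concern.** The plan sets a 30-day recording window, but for one group it schedules no contact at which the end of that window is asked about. The group is subjects who stop for progression and start new cGVHD therapy before Day 30. Events after their last listed AE review depend on spontaneous report, unscheduled contact, or the site's own initiative at a survival call.

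Switching is plausible here. Protocol 1.5 cites a retrospective second-line cohort with 56% failure-free survival at 6 months and treatment change as the main cause of failure. That figure does not show how many subjects in this trial would switch before Day 30.

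At the analysis stage, the added words in SAP 6.1 can be read in two ways, so two programmers could build different AE tables from the same data. A typical event at stake is a non-fatal infection that begins after the switch and is judged unrelated to ibrutinib.

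**Working it through.** The plan gives no figure to reproduce. The check is day counting and a comparison of texts.

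**1. Days without a listed AE question.** If the last listed review is on Day d, the uncovered part of the window is 30 − d.

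| Last AE review | Uncovered days |
|---|---|
| Day 1 | 29 |
| Day 7 | 23 |
| Day 14 | 16 |
| Day 20 | 10 |

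**2. Next scheduled contact.** Take 3 months as 91 days. The earliest contact is 91 − 14 = 77 days after the anchor under 8.3.2, and 84 − 7 = 77 days under Appendix A. It therefore falls after Day 30 in every case. Section 8.3.2 does not say whether the interval runs from progression or from the End-of-Treatment visit.

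**3. Recall if AEs were asked about at that contact.** Let E be the End-of-Treatment day, taken from 1 to 22 (the regular window opens on Day 30 − 7 = 23). Let d be the onset day, with E < d ≤ 30.

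- 8.3.2, counted from the End-of-Treatment visit: contact on Day E + 77 to E + 105. Shortest recall (E = 1, d = 30): 1 + 77 − 30 = 48 days. Longest (d = E + 1): 105 − 1 = 104 days.
- 8.3.2, counted from progression, assumed on Day 0: contact on Day 77 to 105. Shortest: 77 − 30 = 47 days. Longest: 105 − (E + 1), which is 103 days for E = 1 and 82 days for E = 22.
- Appendix A, counted from the End-of-Treatment visit: contact on Day E + 77 to E + 91. Shortest 48 days; longest 91 − 1 = 90 days.

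Overall this is 47 to 104 days, roughly 7 to 15 weeks. For comparison, on-drug AE reviews from Week 25 to Week 37 and beyond are 12 × 7 = 84 days apart (protocol 8.2). The longest recall exceeds that by 104 − 84 = 20 days.

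**4. Treatment-emergent cutoff, new therapy on an assumed Day t before Day 30.**

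| t | Protocol 10.5 | SAP, whichever is earlier | Difference (30 − t) | SAP, 30 days after new therapy |
|---|---|---|---|---|
| 1 | Day 30 | Day 1 | 29 fewer days | Day 31 |
| 8 | Day 30 | Day 8 | 22 fewer days | Day 38 |
| 22 | Day 30 | Day 22 | 8 fewer days | Day 52 |

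The last column moves the cutoff but adds no required data. Routine eCRF recording ends on Day 30. After that, 11.4.2 asks only for related SAEs, and related events count in both documents whatever their date. New malignancies are collected throughout follow-up (11.4.6) but have their own summary in SAP 6.1.2.

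**5. Which events are affected.** Remove drug-related events and worsening baseline conditions, which both documents count without regard to the cutoff. Under the whichever-is-earlier reading, what remains is new-onset events judged unrelated that start between the switch and Day 30.

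**6. Scale.** With about 40 treated subjects, one subject moves an AE incidence by 1/40 = 2.5 percentage points. The documents give no count of early switchers, so no study-level effect can be computed.

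**The case against.** The strongest reply is that collection is already required and is not tied to visits. The AE row of Appendix A is continuous to Day 30. Section 11.4.1 asks for AE assessment at every evaluation timepoint and accepts events found by any means. Section 11.4.6 shows that survival contacts already carry one safety item, new malignancies. Deaths within 30 days, later related SAEs and major hemorrhage have their own rules (11.4.2, 11.4.4). The Appendix A column header also puts the End-of-Treatment visit at 30 days.

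Much of this stands. A reader might infer that AE recording lapses at the switch; the documents say the opposite, and the gap is only in scheduled asking. Subjects who stop for other reasons are also largely covered, because 11.4.1 applies at their 12-weekly clinic visits. What does not stand is that progressors are covered too. Section 11.4.1 does not say whether a survival telephone call is an evaluation timepoint, and it adds no contact. Section 11.4.6 names the one item it wants collected after progression; AEs through Day 30 have no matching instruction. The Appendix A header does not remove the early visit that 8.2.2 allows.

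On the cutoff, it can be argued that ending treatment-emergence at the switch is coherent: the cutoff and an early End-of-Treatment visit then roughly coincide, before a second immunosuppressant clouds attribution, and protocol section 10 leaves details to the SAP. That is a defensible choice, but the SAP does not clearly make it. Its AE date-imputation rule (SAP 3.3.2) refers only to 30 days after the last dose.

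**Conclusion.** Both parts hold, and both are minor.

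- **Ascertainment.** For subjects who progress and switch before Day 30, up to 29 days of the recording window have no scheduled AE question when the last review is on Day 1. The next scheduled contact always falls after the window.
- **Analysis.** SAP 6.1 conflicts with protocol 10.5 in its effect only if its wording means whichever date is earlier. It then drops new-onset events judged unrelated that start between the switch and Day 30.

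Two stronger inferences are not supported. A reader might conclude that the tables differ under either reading of SAP 6.1. They should not, because a cutoff later than Day 30 reaches no unrelated events that must be recorded. A reader might also conclude that the trial's safety findings are materially distorted. Nothing in the documents shows how many subjects are affected, and the safety analysis is descriptive.

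The day counts rest on 3 months taken as 91 days, End-of-Treatment visits on Day 1 to 22, illustrative switch days, and, for one anchor, progression on Day 0.

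**What to change.** 1. In protocol 8.3.2 and the Survival Follow-up column of Appendix A, add: if the End-of-Treatment visit took place before Day 30, ask about and record AEs and SAEs with onset through Day 30 at the first follow-up contact already scheduled.
2. In SAP 6.1, set the treatment-emergent cutoff at 30 days after the last dose, as in protocol 10.5. Flag events that start on or after new cGVHD therapy so that they can be tabulated separately.

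The cost is one protocol sentence, one Appendix A entry, one SAP sentence, one flag, and a few minutes at an existing contact. No visit is added. The price of using a scheduled contact is some recall error over roughly 7 to 15 weeks, compared with the 12 weeks already accepted between later on-drug reviews. Some post-switch events may be due to the new therapy, which is the reason for the flag.

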8.3. Follow-up Phase

Once a subject has completed the End-of-Treatment Visit they will enter the Follow-Up Phase (Visits every 12 Weeks).

8.3.1. Response Follow-up

Subjects who discontinue the study for reasons other than progressive disease will be followed every 12 weeks (± 7 days) by clinic visit until progressive disease. During this period, the following procedures will be performed:

- Symptom-directed physical examination
- Vital signs and performance status (KPS)
- Hematology
- Serum chemistry
- Donor/host chimerism testing cGVHD NIH Form assessment ([Appendix F](#) and [Appendix G](#))
- Lee cGVHD Symptom Scale ([Appendix E](#))
- Photographic imaging of cGVHD
- Review corticosteroid requirements and any new cGVHD treatment if applicable

8.3.2. Long-Term Follow-up

Once subjects progress (for subjects who have not withdrawn consent), they will be contacted approximately every 3 months (± 14 days) by clinic visit or telephone to assess survival. Subjects will be contacted until death, subject withdrawal, lost to follow-up, or study termination by the Sponsor, whichever occurs first.

9. SUBJECT COMPLETION AND WITHDRAWAL

9.1. Completion

A subject will be considered to have completed the study if he or she has died before the end of the study, has not been lost to follow up, or has not withdrawn consent before the end of study.

9.2. Withdrawal from Study Treatment

Study treatment will be discontinued in the event of any of the following events:

- cGVHD progression (see definition in [Section 7.2.1](#))
- Unacceptable toxicity: an intercurrent illness or AE that prevents further ibrutinib administration.
- Noncompliance with study medication.
- Investigator's decision (such as chronic noncompliance, significant protocol deviation, or best interest of the subject)
- Withdrawal of consent for treatment by subject
- Malignancy progression/relapse.
- Subject's condition no longer requires study treatment.
- Subject becomes pregnant
- Study termination by Sponsor
- Death

All subjects, regardless of reason for discontinuation of study treatment will undergo an End-of-Treatment Visit and be followed for progression and survival.

9.3. Withdrawal from Study

Withdrawal from study (including all follow-up) will occur under the following circumstances:

- Withdrawal of consent for follow-up observation by the subject
- Lost to follow-up
- Study termination by Sponsor
- Death

If a subject is lost to follow-up, every reasonable effort should be made by the study site personnel to contact the subject. The measures taken to follow up should be documented.

When a subject withdraws before completing the study, the following information should be documented in the source documents:

- Reason for withdrawal;
- Whether the subject withdraws consent (ie, withdraws consent to treatment and all further contact) or withdraws consent to treatment but agrees to participate in follow-up visits.

10. STATISTICAL METHODS AND ANALYSIS

Statistical analysis will be done by the Sponsor or under the authority of the Sponsor. A general description of the statistical methods to be used to analyze the efficacy and safety data is outlined below. Specific details will be provided in the Statistical Analysis Plan (SAP).

The primary analysis for all efficacy and safety endpoints will be conducted at approximately 12 months after the last subject's first dose of study drug.

10.1. Subject Information

The following definitions will be used for the safety and efficacy analysis, respectively:

- **Safety population:** All enrolled subjects who receive at least one dose of study drug.
- **Efficacy population:** All enrolled subjects who receive at least one RP2D of study drug.

Additional analysis populations, which might be used for sensitivity analyses and biomarker studies, are defined in the SAP.

